The sponsor has requested expedited review in order to ensure funds are available for this project.

3. Is the research taking place at or using data from any of the following:

Knowing when UT's external clinical partners are involved helps inform IRB review and reporting.

- None of these
- Health Discovery Labs
- Central Health

- CommUnity Care
- Ascension locations → *Submit a request to the [Seton Site Approval Tool \(SAT\)](#) and upload the confirmation email that states the request has been submitted in UTRMS under "Other Documents." Please note, we do NOT need the final approval letter (you will not receive SAT approval until after IRB approval is granted). If you encounter issues or have questions about SAT, please reach out to [contact].*

4. Research Hypotheses

Please describe the research aims and hypotheses in the box below. Note: Procedures will be explained in a separate section below.

Aim 1: To assess the efficacy of lumateperone 42 mg administered once daily compared with placebo in the treatment of patients with Major Depressive Disorder and early life abuse, as measured by change from baseline to end of Week 6 in MADRS total score.

Aim 2: To assess neurocircuitry encoding of threat and reward learning as predictors of lumateperone response and as mechanisms of treatment action, and assess the change from pre-dose to post-dose of task-evoked brain activation.

Aim 3: MADRS response rate (proportion of subjects with an improvement $\geq 50\%$ in the Baseline MADRS total score) at Week 6 of Lumateperone as compared to Placebo.

Aim 4: MADRS remission rate (proportion of subjects with a MADRS total score ≤ 10) at Week 6 of Lumateperone as compared to Placebo.

Aim 5: To assess the efficacy of lumateperone 42 mg administered once daily compared with placebo in the treatment of patients with Major depressive Disorder and early life abuse, as measured by change from baseline to end of Week 6 in Clinical Global Impression-Severity (CGI-S) score.

5. Study Background

Provide the rationale and the scientific or scholarly background for the proposed activity, based on existing literature (or clinical knowledge). Describe the gaps in current knowledge that the project is intended to address.

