The neurocircuitry implicated in altered threat and reward learning as mechanisms of risk for MDD includes the salience network (dorsal anterior cingulate cortex and anterior insula) and striatum. Notably, this neurocircuitry overlaps with dopaminergic and serotonergic pathways targeted by atypical antipsychotic medications^{15,16}. As such, altered neurocircuitry encoding of threat and reward learning could potentially be predictive of clinical outcomes for adjunctive therapies that target these pathways, such as lumateperone. There are two main routes by which these pathways could have clinically predictive significance. First, individual differences in neurocircuitry encoding of threat and reward learning could operate as markers of who would vs would not benefit from lumateperone adjunctive therapy. Second, pre- to post-treatment changes in neurocircuitry encoding of reward and threat learning could operate as a mechanism of symptom reduction (e.g., lumateperone induced improvements in reward and threat neurocircuitry encoding mediate reductions in depression symptoms). These possibilities are not mutually exclusive, and both would have considerable clinical significance for enabling precision medicine approaches to the treatment of MDD among early life trauma populations.

6. Design and Methodology

Provide a brief description of the overall study design or data collection methodologies. Details regarding protocol specific research procedures will be discussed in the next section below.

This is a single site investigator initiated randomized, double-blind, placebo controlled, fixed-dose study in patients with a primary diagnosis of MDD, a history of early life abuse, and who have an inadequate response to on-going SSRI treatment. The study will enroll a total of 50 participants (n=50) with 25 randomized to treatment and 25 to a placebo, and will be conducted in 3 phases:

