Screening Period - After signing the ICF, an identification number will be assigned to the subject. Prior to randomization, all subjects will enter a 2 week-day screening period (Screening) to determine eligibility. Eligible subjects must meet the Diagnostic and Statistical Manual of Mental Disorders, Fifth Edition (DSM-5) criteria for MDD without psychotic features, based on the DIAMOND (Diagnostic Interview for Anxiety, Mood, and Other Neuropsychiatric Disorders), with a current major depressive episode of at least 8 weeks in duration. They must have had an inadequate response (<50% symptom reduction) to an adequate trial of at least 1 antidepressant therapy (ADT) (as determined by administering the Massachusetts General Hospital Antidepressant Treatment History Questionnaire [ATRQ]) in their current Major Depressive Episode (MDE). During Screening Period (2 weeks) patient eligibility will be assessed and a Pre-dose fMRI performed.

Double-blind Treatment Period - Double-blind Treatment Period (6 weeks) during which all eligible patients will be randomized to receive lumateperone 42 mg or placebo in 1:1 ratio. At Baseline (Visit 2), patients who continue to meet all eligibility criteria will be randomized to either lumateperone or placebo.

Safety Follow-up Period in which all patients will return to the clinic for a safety follow-up visit approximately one week after the last dose of study treatment. All patients will complete a post dose MRI 1 week after the 6-week study period is completed.

- During the Pre-Dose and Post-dose MRI, Participants will undergo standard structural imaging as well as functional imaging during computational threat and reward learning tasks. Computational neuroimaging approaches will characterize neurocircuitry encoding of anticipating and delivery of threat and reward outcomes, enabling testing of predictors of lumateperone clinical response and mechanism of treatment action.

- Patients who discontinue study drug prior to Week 6 but agree to continue participation in the Double-blind Treatment Period (DBTP) should be seen at all subsequent protocol-defined visits up to week 6 and should also return for the SFU Visit for post dose MRI. Study drug will no longer be dispensed for these patients and the clinical management of these patients will be at the discretion of the Investigator.

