11.2 Statistical And Analytic Plan

The primary efficacy endpoint is the change from baseline to end of Week 6(EOT) in MADRS total score. Based on the primary hypothetical estimand strategy which assumes patients are on study drug up to the primary time point (end of Week 6), MADRS assessments collected off-treatment (ie, efficacy assessment performed more than 3 days after last dose of study drug) and/or after starting new treatment for MDD will be set to missing (except those collected for patients discontinued due to and will not be included in the primary analysis). The missing data in patients who discontinued due to lack of efficacy (LOE) or due to taking non-study treatment for MDD will be assumed missing-not-at-random. The missing data in patients who discontinued due to other reasons will be assumed as missing- at-random. Missing data will be imputed accordingly to recent recommendations using the ‘mice’ package in R.^{25,26}

The primary analysis will use a mixed-effects model for repeated measures (MMRM) to analyze the change from baseline to end of Week 6 in MADRS total score. Similar MMRM models will be used for secondary endpoints. An additional analysis will examine slopes of MADRS scores over the 6 week period, testing the hypothesis that the active drug group will have a steeper slope of MADRS over the 6 week period. Additional models will test for non-linear patterns of change as well. Similar analyses will be conducted on secondary outcomes (e.g. CGI, PTSD

symptom severity, etc.).

For imaging data, following standard preprocessing, beta coefficients of voxelwise brain activity will be defined using standard general linear models. These coefficients will be used in multivariate pattern analysis (MVPA) to build classifiers, using support vector machines (SVM), of reward and threat using leave-one-out cross-validation and quantify reward and threat anticipation during the task. MVPA classifier output will be analyzed using mixed effects models. Threat and reward anticipation as predictors of treatment outcome will be analyzed by including these variables as a predictor in the MMRM described above. Threat and reward anticipation as targets of treatment will be analyzed in mixed effects model with post-treatment classifier output as the dependent measure and including predictors of drug group and including pre-treatment classifier output as a covariate.

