11.4 Efficacy Estimand Analysis

Main estimands are defined for the primary efficacy variable:

- Absolute change from Baseline to Week 6 of the MADRS total score

and for the following 3 key secondary efficacy variables in hierarchical rank order of the hypothesis testing procedure:

- MADRS response rate (proportion of subjects with an improvement $\geq 50\%$ in the Baseline MADRS total score) at End of Treatment (EOT) Week 6, Lumateperone as compared to placebo

- MADRS remission rate (proportion of subjects with a MADRS total score ≤ 10) EOT Week 6, Lumateperone as compared to placebo

- Change from Baseline to EOT Week -6 in the Clinical Global Impression of Severity (CGI-S) score, Lumateperone as compared to placebo

Confirmatory testing will be performed only for these main estimands, whereby the testing of the key secondary estimands will follow the ordered hierarchical approach.

The primary statistical analysis of all confirmatory tested estimands will be performed on the Total Population, using the mixed-effect model repeated measure (MMRM) analysis. For the main primary estimand, the changes from baseline in MADRS total score will be analyzed using a Mixed Model with

Repeated Measures (MMRM). This model will include Treatment, Visit, Treatment-by-Visit interaction and the number of failed prior treatments (1 or more than 1) as fixed effects, Baseline value as a covariate, and Visit as the repeated effect. The estimated means for each arm as well as the estimated treatment effect (Lumateperone – Placebo) along with the 95% confidence intervals for the treatment effect will be presented for each visit. The primary estimand will be estimated as the difference between treatment means (MMRM least-squares) at the EOT Week 6 (Visit 7).

As a sensitivity analysis for all estimands, the MMRM analysis will be performed using a range of missing value imputations. For the main estimand of the primary efficacy, a tipping point analysis will be applied to investigate the robustness of the analysis results.

Study Elements Requiring Additional Information or Approvals

9. Public Registration and Reporting Requirements

Federal regulations, policy, and some journal guidelines require public registration and results reporting for studies that meet the definition of a clinical trial.

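### Aim 2 asks whether brain encoding predicts response to lumateperone, but the stated model has no marker-by-treatment term and, read plainly, tests prognosis

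*Protocol*

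**What the plan says.** Protocol section 4 (Research Hypotheses), Aim 2, sets out to assess "neurocircuitry encoding of threat and reward learning as predictors of lumateperone response and as mechanisms of treatment action". Section 6 (Design and Methodology) describes the computational imaging as "enabling testing of predictors of lumateperone clinical response and mechanism of treatment action". Section 5 (Study Background), in text repeated in section 22, gives the predictor half its meaning: individual differences in encoding "could operate as markers of who would vs would not benefit from lumateperone adjunctive therapy".

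The analysis for that half is one sentence in section 11.2: "Threat and reward anticipation as predictors of treatment outcome will be analyzed by including these variables as a predictor in the MMRM described above". The only list of MMRM terms is in section 11.4, for the main primary estimand: "This model will include Treatment, Visit, Treatment-by-Visit interaction and the number of failed prior treatments (1 or more than 1) as fixed effects", with the baseline value as covariate. Treatment-by-visit is its only interaction. The other imaging model in section 11.2 regresses post-treatment classifier output on drug group, adjusted for the pre-treatment output. It addresses mechanism, not who benefits.

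Section 11.4 limits the formal tests: "Confirmatory testing will be performed only for these main estimands". Those are the MADRS change and three key secondary endpoints, so Aim 2 lies outside them.

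**The concern.** Who benefits from a drug is a question about effect modification. In a placebo-controlled trial it is answered by asking whether the drug-placebo difference changes with the marker, which needs a contrast of slopes between arms. A marker entered as one more predictor gets a single slope common to both arms, and that is a measure of prognosis.

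Two errors could follow. A marker that predicts improvement equally on drug and placebo could be reported as predicting lumateperone response. A marker whose relation to outcome reverses between arms would average out and be missed. The background ties this question to precision medicine, so the distinction decides what the imaging results may be said to show.

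**Working it through.** **Inputs.** 50 patients, 25 per arm, 1:1 (sections 6 and 15). Five post-baseline visits in the treatment period (Visits 3-7, section 4.2.3), with the primary time point at Week 6, Visit 7. Section 16 says only that power is moderate. There is no marker effect, SD or power figure for Aim 2, so there is no figure of the plan's to reproduce. Assumed: marker SD 1, residual SD 1, a Week 6 outcome adjusted for baseline, two-sided 5% (the protocol gives no alpha but reports 95% intervals). Slopes are in outcome SD per marker SD.

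**What each coefficient estimates.** Let the Week 6 slope on the marker be bL on lumateperone and bP on placebo. With 1:1 randomisation the marker has the same expected spread in each arm, so:

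- additive coefficient = (bL + bP)/2
- marker-by-treatment coefficient = bL - bP

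Aim 2 concerns the second. Slopes of 0.4/0.4, 0.6/0.2 and 0.8/0.0 all give (bL + bP)/2 = 0.40, while bL - bP is 0, 0.4 and 0.8.

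**Simulation.** 20,000 trials per scenario; least squares on treatment, baseline and marker, with and without marker-by-treatment.

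| Slope, lumateperone / placebo | Additive coefficient | Additive test positive | Interaction coefficient | Interaction test positive |
|---|---|---|---|---|
| 0.4 / 0.4 | 0.40 | 75% | 0 | 5% |
| 0.6 / 0.2 | 0.40 | 74% | 0.4 | 26% |
| 0.8 / 0.0 | 0.40 | 68% | 0.8 | 74% |
| +0.4 / -0.4 | 0.00 | 6-7% | 0.8 | 73% |
| 0.3 / 0.0 | 0.15 | 17% | 0.3 | 17% |
| 0.5 / 0.0 | 0.25 | 37% | 0.5 | 37% |

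With no marker effect both tests are positive in 5%. A separate run of 10,000 trials, without the baseline covariate, agreed: reversed slopes of 0.4 gave 6.6% and 75%, and a drug-only slope of 0.5 gave 38% and 37%.

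**Equally prognostic marker, total outcome SD 1.** At marker-outcome correlations of 0.1, 0.2, 0.3 and 0.4 the additive test is positive in 10%, 28%, 56% and 82%; the interaction stays at 5%. With two such markers tested separately (correlated 0 or 0.5 with each other), at least one additive result is positive in 42-49% at correlation 0.2 and 73-81% at 0.3, against 9-10% for the interaction.

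**Precision of the right contrast.** For a normally distributed marker, SE = sqrt(2/(25 - 3)) = 0.30. With 50 - 5 = 45 degrees of freedom the 95% half-width is 2.014 x 0.3015 = 0.61. Simulated power is 74%, 78% and 82% at slope differences of 0.8, 0.85 and 0.9. The normal approximation is slightly optimistic: 80% power at 2 x (1.960 + 0.842)/sqrt(50) = 0.79. With 20 evaluable per arm (assumed), SE = sqrt(2/17) = 0.34, the half-width is 2.03 x 0.343 = 0.70, and 80% power is reached only at a difference of 1.0.

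**The case against.** The strongest reply is that this is detail for the statistical analysis plan. Whether a predictor enters alone or crossed with treatment is often left there, and the sentence does not rule out an interaction. The term list in section 11.4 belongs to the confirmatory model, where nobody would expect a marker term. Section 11.2 also speaks of treatment outcome rather than lumateperone response, and an additive term does answer that narrower question.

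Part of this stands. The section 11.4 list is weak evidence, and the point does not depend on it. But the protocol is not silent: it says how the question will be analysed, and an analysis plan that followed it literally would carry the mismatch forward. If prognosis was all that was meant, no analysis serves the first half of Aim 2. The same section names drug group in the mechanism model, so the omission here is visible.

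A second reply concerns the percentages, and it is right. A single marker coefficient in the MMRM is pooled over five visits as well as over arms. In five-visit simulations of the 0.4/0.4 case, the additive coefficient was 0.40 (positive in 86-98%) if the marker effect is constant over visits, about 0.24 (45-69%) if it grows linearly to Week 6, and 0.12-0.16 (16-31%) if it appears only at the last two visits. The Week 6 figures above are therefore illustrations, not the plan's error rates. Pooling over visits does not turn a coefficient averaged over arms into a contrast between them.

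Third, the stakes are limited: the aim is outside the confirmatory tests, and a drug-only marker is detected about equally often either way. That is also true. The gain is correct interpretation, not power.

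**Conclusion.** The concern holds. The protocol asks who responds to lumateperone and states an analysis that, on its plain reading, estimates prognosis pooled over arms. That follows from the model and needs no assumed effect size. The percentages rest on the Week 6 assumptions listed and serve only to show scale: the same additive coefficient of 0.40 arises from no effect modification and from a marker that works only on drug, and reversed slopes are found in 6-7% of trials against 73% with the interaction. The primary and key secondary results are not touched. The wording should be corrected before analysis, because a stated aim depends on it.

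**What to change.** In section 11.2, state for each marker (threat and reward, in separate models, using the pre-dose scan) a marker-by-treatment contrast at Week 6 (Visit 7). Base any statement about predicting lumateperone response on that contrast with its 95% confidence interval, labelled exploratory. Report the marker main effect as prognostic only.

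Two routes are open:

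- **Single Week 6 model.** Adds 2 coefficients per marker (marker, marker-by-treatment). It uses only patients with a Week 6 value unless it is run on the imputed data.
- **Full MMRM.** Adds 10 coefficients per marker (marker-by-visit and marker-by-treatment-by-visit, five each), which is heavy for 50 patients.

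With complete data and all terms crossed with visit, the two routes gave the same Week 6 contrast to rounding error in 200 simulated data sets. With one common baseline slope they correlated 0.996 and had the same SD (0.30). The lighter model therefore loses little when data are complete.

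The cost is in interpretation. No new data, visits or scans are needed, but the contrast will be imprecise, with 80% power only for a slope difference between 0.85 and 0.9 SD at 25 per arm. Two markers each tested at 5% give about 1 - 0.95 x 0.95 = 9.75% chance of at least one false positive (9-10% in simulation). Both are reasons for the exploratory label.

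### Aim 2 promises a test of mechanism, but the model fixed for it tests only whether the drug changes the brain measure; no stated model relates pre-to-post neural change to MADRS change

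*Protocol*

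**What the plan says.** **The aim.** Item 4 (Research Hypotheses) states Aim 2 as assessing "neurocircuitry encoding of threat and reward learning as predictors of lumateperone response and as mechanisms of treatment action". The same sentence adds a further component, the change in task-evoked activation from before to after dosing.

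**The design claim.** Item 6 (Design and Methodology) describes the imaging as "enabling testing of predictors of lumateperone clinical response and mechanism of treatment action".

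**What mechanism means here.** Item 5 (Study Background), repeated in item 22, offers two routes to clinical significance. The second is change in encoding as a mechanism of symptom reduction, illustrated as "lumateperone induced improvements in reward and threat neurocircuitry encoding mediate reductions in depression symptoms".

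**The analyses.** Section 11.2 ties two models to these purposes:
- Prediction: "Threat and reward anticipation as predictors of treatment outcome will be analyzed by including these variables as a predictor in the MMRM described above".
- Targets of treatment: a "mixed effects model with post-treatment classifier output as the dependent measure and including predictors of drug group", with pre-treatment classifier output as covariate.

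**Timing and size.** Item 6 says: "All patients will complete a post dose MRI 1 week after the 6-week study period is completed". The primary endpoint in section 11.3 is MADRS change to Week 6 (Visit 7). Allocation is "25 randomized to treatment and 25 to a placebo".

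**The concern.** As the background describes it, mechanism has two links: the drug changes the neural measure, and that change accounts for the fall in symptoms. The targets-of-treatment model estimates the first link only. A drug effect on classifier output is equally compatible with a neural change that drives improvement and with one that is a by-product of the drug unrelated to mood.

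The predictor model does contain MADRS, but it is set up to ask whether anticipation signals predict outcome. Nothing in section 11.2 enters pre-to-post change, and no indirect effect is mentioned anywhere in the protocol.

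What is at stake is the interpretation of Aim 2. A significant group effect on classifier output would fall under an aim worded as mechanism, although the analysis behind it cannot tell mechanism from by-product.

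**Working it through.** The plan gives no figure for this analysis, and item 16 gives no effect size, alpha or power value, so there is nothing to reproduce. The check sets aim against model, then shows the consequence under stated assumptions.

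**1. Aim against model**

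| Component of Aim 2 | Model in section 11.2 | MADRS in the model? | Neural change related to MADRS change? |
|---|---|---|---|
| Predictor of response | Anticipation measures added to the MADRS MMRM | Yes | No, not stated |
| Pre- to post-dose change | Post output on group, adjusted for pre output | No | No |
| Mechanism of treatment action | None beyond the row above | No | No |

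**2. What the stated model can distinguish**

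Assumed inputs: 25 per arm (item 6), two-sided alpha 0.05, pre-post correlation 0.5, drug effect on the brain measure 0.7 SD of the post-treatment measure, 4,000 runs per scenario. MADRS is on a scale with residual SD 1. The direct drug effect c was chosen so that, outside the first row, the total effect 0.7 × b + c stays near −0.6.

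- Stated model: post ~ group + pre. Reject if group has p < 0.05.
- Joint test: the stated model rejects and, in MADRS ~ group + post + pre + baseline MADRS, post has p < 0.05. With pre and baseline MADRS in the model, using post output and final MADRS gives the same coefficient for the brain measure as using the two change scores.

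| Brain-to-MADRS path b | Direct effect c | Total effect | Stated model rejects | Joint test rejects |
|---|---|---|---|---|
| 0 | 0 | 0 | 79.7% | 3.8% |
| 0 | −0.6 | −0.60 | 79.5% | 4.5% |
| −0.3 | −0.4 | −0.61 | 79.6% | 31.5% |
| −0.5 | −0.25 | −0.60 | 79.0% | 63.9% |
| −0.8 | 0 | −0.56 | 79.2% | 78.5% |

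The Monte Carlo standard error near 80% is √(0.8 × 0.2 / 4000) ≈ 0.6 percentage points. The stated model's rejection rate therefore does not vary with the brain-symptom path, as expected of a model without MADRS.

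**3. What the missing link could show at this size**

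The proposed model partials out three covariates (arm, baseline MADRS, pre-treatment output). The partial correlation detectable with 80% power, two-sided 0.05, is r = tanh((1.96 + 0.842) / √(n − 3 − 3)).

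- n = 50: tanh(2.802 / √44) = tanh(0.422) ≈ 0.40
- n = 40 (illustrative; the protocol gives no dropout figure): tanh(2.802 / √34) = tanh(0.481) ≈ 0.45

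That covers the brain-symptom path alone. An indirect effect also needs the drug-to-brain path. For an unadjusted two-arm comparison the difference detectable with 80% power is 2.802 × √(2/25) ≈ 0.79 SD. The joint-test column shows the combined cost: even with a 0.7 SD drug effect on the brain measure, about 32% and 64% at the intermediate paths.

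**4. Timing**

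The post-dose scan is at Visit 8 (Week 7), about one week after the last dose and after the Week 6 MADRS. Section 11.2 counts efficacy assessments more than 3 days after the last dose as off-treatment; by that cut-off the scan is off-treatment too. Table 1 also marks a MADRS at Visit 8, while section 7.2.4, which lists that visit's procedures, does not include it.

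**The case against.** Several points on the other side stand.

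- **The model is not misplaced.** It is a sensible analysis of Aim 2's closing clause, and section 11.2 labels it as addressing targets of treatment, which is what it does.
- **Mediation is not a stated hypothesis.** It appears in the background as an example among possibilities, not in item 4. A reader might infer that the trial formally hypothesises mediation and then fails to test it. The documents support less: items 4 and 6 promise a test of mechanism, and the background illustrates what that means.
- **Brain and MADRS are not wholly unconnected.** A reader might infer that the plan never links them. The predictor MMRM does so, and its wording does not restrict it to pre-treatment values. The gap is specific to pre-to-post change.
- **The scan does not follow every MADRS.** It follows the Week 6 endpoint, but Table 1 marks a concurrent one at Week 7.
- **A mediation model would not establish mechanism either**, given the scan timing and 25 per arm.

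It can also be said that an exploratory model belongs in a statistical analysis plan. That would answer silence, but the protocol is not silent: it assigns a model to each imaging purpose, and the one left for treatment action cannot answer the mechanism part of the aim. The prediction that a positive result would be misreported is also not in the plan; the defect is that the aim's wording invites that conclusion.

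**Conclusion.** The concern holds in limited form. The protocol promises a test of mechanism and fixes a model that can show target engagement only; no stated model relates neural change to MADRS change. Under the assumed inputs the stated model rejects at the same rate, about 79–80%, whether the neural change accounts for none or all of the drug's MADRS effect. The level depends on the assumed 0.7 SD effect; the insensitivity to the brain-symptom path follows from MADRS being absent from the model.

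It would be too strong to infer that the missing link is readily estimable from this trial. The brain-symptom path alone needs a partial correlation of about 0.40 to 0.45, and the indirect effect will be less precise than that suggests.

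Section 11.4 restricts confirmatory testing to the MADRS and CGI-S estimands, so the primary and key secondary results are unaffected. The change should be made, but the trial's main conclusion does not depend on it.

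**What to change.** 1. **Add one exploratory model to section 11.2:** MADRS change on change in classifier output, adjusted for arm, baseline MADRS and pre-treatment output. Report the indirect effect with a bootstrap confidence interval.
2. **Label it associative**, stating that the post-dose scan follows the Week 6 endpoint and comes about a week after the last dose.
3. **Reconcile Table 1 with section 7.2.4** on whether MADRS is collected at Visit 8. If it is, use it as a concurrent sensitivity outcome, noting that it too is off-treatment by the 3-day cut-off in section 11.2.
4. **State the expected imprecision** at 25 per arm, with the detectable partial correlations above.
5. **Whether or not the model is added, limit the Aim 2 conclusion to target engagement**, or reword items 4 and 6 accordingly. Only this step removes the mismatch, because the added model cannot by itself establish mechanism.

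The cost is one extra exploratory analysis and a more modest Aim 2 claim. With Week 6 MADRS as the outcome, it uses data the trial already plans to collect.
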